9.4. Study Withdrawal

All patients, including patients discontinued from study treatment, will continue to be followed up for 5 years after randomisation, unless the patient withdraws consent, is lost to follow up or death. The reason for withdrawal should be documented.

10. CONCOMITANT/CONTRAINDICATED MEDICATIONS

Patients are not permitted to take the following medications concurrently with the study drug. If required, patient should be removed from the study treatment with the reason clearly documented: -

- Other investigational drugs while on treatment with study drug
- Any anticancer treatment while on treatment with study drug
- Antiplatelet agents (off-study Aspirin, clopidogrel, ticlopidine) concurrently with study medication
- Anticoagulants (warfarin, unfractionated heparin or low molecular weight heparin) concurrently with study medication

Patients should be encouraged to use paracetamol or codeine phosphate for analgesia and to avoid NSAID whenever possible. Although short term intermittent NSAID use is allowed, NSAID should not be prescribed with study drug for more than 2 consecutive weeks. The use of NSAID must be clearly documented throughout the study.

Patients will be allowed concurrent PPIs, H2 antagonists or antacids.

Ongoing concomitant medication will be recorded from baseline visit date until 30 days after treatment discontinuation. Patients receiving study drug should maintain adequate contraception.

11. ASSESSMENTS AND FOLLOW-UP

11.1. Screening

Within 8 Weeks prior to randomisation

- Haematology: platelet count
- Creatinine
- LFT: serum bilirubin, AST, ALT

Within 16 months prior to randomization

- Full colonoscopy(or CT colonogram).
- Imaging of abdomen (CT or CT colonogram or MRI or PET or Ultrasound)
- Radiological examination of the Chest (including but not restricted to Chest x ray, CT thorax or PET scan)

11.2. Baseline

- Medical history: asthma, diabetes, ischaemic heart disease, stroke, gastrointestinal ulcers or bleeding, alcohol history, smoking
- Tumour History: stage, risk factors, treatment, and tumour response grade (for patients with neoadjuvant chemoradiation only)
- Family history of Colorectal cancer
- Record ongoing medication
- Vital signs: body weight, height, BP
- Haematology: haemoglobin (within 8 weeks prior to randomisation)
- CEA(latest reading)
- Randomization performed and study treatment commence

11.3. 3-monthly assessments

3-monthly patient assessments will be done at month 3, 6, 9, 12, 15, 18, 21, 24, 27, 30, 33, and 36. Assessments \pm 1 month window will be allowed for each 3-monthly visit. Phone assessments are allowed at alternate 3-monthly assessments if patient is unable to return for site follow-up. The following will be performed at each assessment:

- CEA
- Hb (for month 6, 12, 18, 24, 30, 36 only)
- Record AE and SAE (See Section 13.2)
- Concomitant medication
- Concomitant NSAIDs
- Medical Events : (acute myocardial infarction, transient ischemic attack, stroke, new cancers and gastrointestinal bleeding)
- Recurrence and Salvage Chemotherapy

The following will be performed at each specified interval:

- Surveillance Colonoscopy/ CT colonogram at month 6 and 30 (optional) *
- Surveillance CT scan (abdomen \pm pelvis) / or CT colonogram at month 6, 18 and 30 (optional)*

Off-site investigations (for example surveillance CEA, CT scan, colonoscopy) will be allowed and data from unscheduled investigations (for example CT scan or colonoscopy due to symptoms or during hospitalisations) may be recorded.

* The policy of surveillance CT scan and Colonoscopy (as described above) will be decided at the study centre level, by the study centre PI. However, these procedures wherever implemented, should be consistently applied to all trial subjects within a particular study centre.

Early Treatment Discontinuation follow-up

- Subjects with early treatment discontinuation (e.g. for toxicity) but without recurrence will continue with the same 3 monthly assessments except Hb that is not required after study drug treatment is discontinued.
- Subjects with recurrence (who may be receiving salvage treatment or palliative care) may be assessed at 6 monthly intervals in the clinic or via phone assessments if they are unable to return for 3 monthly clinic follow up. Hb, CEA, and concomitant medication data are not required after recurrence date.

11.4. 6-monthly assessments

6-monthly assessments will be done at month 42, 48, 54 and 60.

Assessments \pm 1 month window will be allowed for each 6-monthly visit. The following will be performed at each assessment:

- CEA
- Death and related information if any
- Medical Events: (AMI, transient ischemic attack, stroke, new cancers and gastrointestinal bleeding)
- Concomitant NSAIDs
- Recurrence and salvage chemotherapy
- Subjects with recurrence (who may be receiving salvage treatment or palliative care) may be assessed via phone assessments if they are unable to return for clinic follow up. CEA is not required after recurrence date.

11.5. Unscheduled visits

Any additional visit to the scheduled follow-ups will be considered as unscheduled visit if it is of medical significance in the opinion of the treating physician or investigator.

At such visits, the patient will be assessed for:

- Recurrence
- AE and SAE
- Medical Events: (acute myocardial infarction, transient ischemic attack, stroke, new cancers and gastrointestinal bleeding)

11.6. Assessment of recurrence and salvage chemotherapy

For the patient with unequivocal radiological documented recurrence, the date of CT scan or any other radiological modality documenting unequivocal recurrence will be taken as the date of recurrence. Patients who have disease recurrence confirmed with histology or cytology, the date of recurrence will be taken as the date of biopsy or cytology collection.

For patients with local recurrence detected through colonoscopy/CT colonogram or digital rectal examination (DRE), without CT scan or histology, the date of colonoscopy or DRE will be taken as the date of recurrence.

An elevated CEA level or abnormal LFT will not be considered as acceptable evidence of colorectal cancer recurrence. However, a rising CEA trend should prompt the search for possible tumour recurrence.

At the time of colorectal cancer recurrence, the investigator should clearly indicate the site of tumour recurrence and the method of diagnosis.

Patients with tumour recurrence and commencing salvage chemotherapy will have the names and initiation date of each new chemotherapy regimen recorded.

11.7. Assessment of Medical Events

Medical events such as acute myocardial infarction, ischemic stroke (including transient ischemic attack), hemorrhagic stroke or new non-colorectal cancers will be recorded. Major gastrointestinal bleeding (requiring blood transfusion) will also be recorded.

11.8 Post Month 60 – Clinical Data

Subjects who have consented to allow data collection after month 60, will have their medical records reviewed every 12 months (or via phone contact), up to and at the time of the last patient last visit (month 60 or earlier) - at the site.

The following will be recorded:

- Death related information; if any
- Medical Events: (AMI, transient ischemic attack, stroke, new cancers and gastrointestinal bleeding)
- Concomitant NSAIDs
- Recurrence and salvage chemotherapy

12 STATISTICAL CONSIDERATIONS

12.1 Sample size calculation

Initial sample size calculation

The initial total trial size was 2660 patients, 1330 randomised to Aspirin group and 1330 randomised to Placebo group. In the sub-groups, there should be at least 2000 high risk Dukes B or Dukes C colon cancer patients, others are rectal cancer patients

It was assumed that 3-year disease free survival rate for Dukes B colon cancer, Dukes C colon cancer and rectal cancer are 65% after standard adjuvant chemotherapy; and the attrition rate is 5%. The total trial size (2660) would be sufficient to detect an 6% absolute difference of disease free survival rate for all subjects between the two treatments, with a two-sided logrank test of 5% type I error and 90% power; For the main sub-group analysis, the 3-year DFS rate for colon cancer patients

was assumed to be 65% under standard care, which is similar to the entire group as a whole, the size of colon cancer (n=2000) will be sufficient to detect an 6% absolute difference of disease free survival rate for colon cancer between the two treatments, with a two-sided logrank test of 5% type I error and 80% power.

Subsequent sample size calculation

Based on recent studies^{31,33,34} of aspirin in colorectal cancer patients, with a reported hazard ratio (HR) or risk ratio ranging from 0.67 to 0.77, we assumed a hazard ratio of 0.72 for disease free survival between the aspirin and the placebo groups. The corresponding absolute difference of disease free survival rate between the two treatment groups is about 8.5% instead of 6% for a 3 year disease free survival rate of 65% in the placebo group. To detect a HR of 0.72, a total of 300 recurrences (or deaths if occur without recurrence) is required for a two-sided logrank test of 5% type I error and 80% power. This translates into a total sample size of 1200 patients if the disease free survival rate is 65% in the placebo group and attrition rate is 15%.

Latest sample size calculation

A recent review of trial interim data, after enrollment of at least 1140 patients and 3-years follow-up being completed in 430 patients, revealed a pooled disease free survival rate of 79% at 5 years. We estimated that only 240 recurrences would be observed with a total sample size of 1200, a shortfall of 60 recurrences to maintain the study power at 80%. We subsequently recalculated the sample size to be 1587 patients such that we would expect to observe 300 recurrences (or deaths) at the end of study (attrition rate reduced from 15% to 10%, the rest unchanged).

12.2 Statistical analysis

All statistical analyses will be carried out on an intention-to-treat basis.

In the analysis of disease free survival, an event of interest is considered to have occurred if a patient relapses or dies during the study period. The starting point for disease free survival is the date of randomisation and the end point is the date of first disease recurrence or date of death, whichever occurs first. Patients in whom there has been no evidence of disease after treatment are censored at the date of last follow-up. Similarly, the overall survival time is censored at the date when the patient is last known to be alive.

Each primary endpoint will be analysed as follows. Survival curves will be constructed using the Kaplan-Meier method. Life table estimates of 3 and 5 year survival rates will be calculated. The efficacy of Aspirin will be evaluated by the Hazard Ratio (HR) and its corresponding 95% CI. A Cox proportional hazard model will be used to estimate HRs adjusting for the trial stratification factors (site, type of tumour and type of adjuvant chemotherapy). Stratified analysis and other non-proportional hazard models (which allow for the effects of covariates to vary over time) would be considered when proportional hazards assumption is not valid.

The secondary endpoint of overall survival will be analysed in a similar manner to the primary endpoints. For the subgroup analyses, tests for interaction for the colon cancer subgroups and other subgroups will be conducted first. Similar analyses of DFS and OS as presented above will be repeated within the subgroups respectively defined by ethnicity, tumour type, and patients'

compliance and according to patient's PIK3CA mutational status. The percentage of patients with different PIK3CA mutational status will be compared by Chi-square test in the Aspirin and Placebo groups.

As an exploratory analysis, cumulative incidence function will be estimated and the two treatment arms will be compared using Gray's method when considering competing risks of first recurrence with different causes of death due to colorectal cancer, other cancers or other causes.

12.3 Interim analysis

An independent DMC will be established to review the interim results of the study. Two interim analyses are scheduled. Ideally, the first interim analysis should be done after 540 patients have been recruited (estimated to take between two to three years) or at the mid-point of the targeted recruitment period (end of Year 2012), whichever comes earlier. The second interim analysis should be done once 540 patients or the same cohort of patients from the first interim analysis, have been followed up for 3 years (approximately between fifth to sixth year).

The aim of the first interim analysis is toxicity. Safety will be the main issue reviewed in the first DMC meeting. A report containing non-confidential data should be sent to the Study Steering Committee. Randomisation, compliance, CRF received and processed, AE and SAE should be included in this DMC report.

The study endpoints to be reviewed in the second interim analysis are disease free survival and overall survival, in addition to toxicity profiles. Statistical analysis method for the primary endpoint will be the same as 12.2. The analysis results of the interim analyses will not be the sole criteria for deciding whether to terminate accrual or report the results early. Rather they will provide a guideline to aid in the decision, which will also take into account the characteristics of the patients, nature of toxicities, relevant external results. Another goal of this monitoring is to identify if the study is underpowered and sample size needs to be adjusted. Apart from the reason of safety, which may caution otherwise, the minimum trial size will remain as 1200 as initially planned.

In addition to the two interim analyses above, periodic review of safety data (in the same format of the first interim analysis) will be performed for annual DMC meetings. Efficacy data will not be included unless requested by DMC.

The results of the interim reviews will remain confidential to the study statistician and the DMC members. After reviewing the efficacy and safety data, the DMC will make recommendations to the Study Steering Committee on changes to the protocol.

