A recent review of trial interim data, after enrollment of at least 1140 patients and 3 year follow-up being completed in 430 patients, revealed a pooled disease free survival rate of 79% at 5 years, we subsequently recalculated the sample size to be 1587 patients (attrition rate reduced to 10%, the rest unchanged).

In analyzing the Primary Endpoint: Disease Free Survival (DFS) and Secondary Endpoint: Overall Survival (OS), logrank test will be used to compare between groups. Hazard ratio and its 95% confidence interval will be estimated. Cox model will be further performed to adjust for potential confounding factors.

Two interim analyses are scheduled. The first analysis is a safety and toxicity analysis planned to be done after 540 patients are recruited into the study or at the mid-point of the targeted recruitment period, whichever comes earlier. The second analysis will look at safety as well as DFS and OS, after 540 patients have been followed up for 3 years, or when the cohort of patients included in the first analysis have completed follow up for 3 years..

ICR02 /ASCOLT

Assessments	Screening*		Baseline	Follow-up month (+/- 1 month)			Follow-up month (+/- 1 month) After Recurrence	Follow-up month (+/- 1 month) After Early Study Drug Discontinuation and no recurrence	Post Month 60	
				3, 9, 15, 21, 27, 33	6,12, 18, 24, 30, 36	42, 48, 54, 60	3 to 60	3 to 36		
Written informed consent		x								
Demography, Tumour history, Medical history & family history			x							
Record surgical measurements,(For rectal cancer only)			x							
Adjuvant Therapy			x							
Vital signs (Body weight, BP, height), ECOG			x							
Hb	(Within 8 weeks prior to randomisation)		x		x					
Platelet count, Creatinine, Serum Bilirubin, AST, ALT	(Within 8 weeks prior to randomisation)	x								
CEA			x	x	x	x		x		
Imaging of abdomen (CT or CT colonogram or MRI or PET or Ultrasound)	To be done if not done within 16 months prior to randomization	x		x (Mth 6, 18 and 30) Optional; or frequency according to institutional practice						
Radiological examination of the Chest (including but not restricted to Chest x ray, CT thorax or PET scan)	To be done if not done within 16 months prior to randomization	x								
Colonoscopy/CT colonogram	Full colonoscopy if not done within 16 months prior to randomization	x		x (Mth 6 and 30) Optional; or frequency according to institutional practice						
AE and SAE				x	x					
Death				x	x	x	x	x	x	
Medical Events				x	x	x	x	x	x	

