4.8 Interim Analysis

Interim analyses were scheduled every year as long as there is subject still on study treatment. An independent Data Monitoring Committee (DMC) was established to review the interim results of the study. Ideally, the first interim analysis should be done after 540 subjects have been recruited or at the midpoint (end of Year 2012) of the targeted recruitment period, whichever comes earlier. The second interim analysis should be done once 540 subjects have

been followed up for 3 years (approximately between fifth to sixth years). Treatment allocations in all the interim analyses were masked with the label “Group A” and “Group B”.

Safety was the main aspect for review in the first DMC meeting. A report containing non-confidential data was sent to the Study Steering Committee. Randomisation, compliance, CRF received and processed, AE and SAE were included in this DMC report. The study endpoints reviewed in the second interim analysis were DFS and OS, as well as safety profiles. Subsequent reviews of DFS and OS were done upon request of DMC.

The analysis results of the interim analyses were not the sole criteria for deciding whether to early terminate the study. Rather they provided a guideline to aid in the decision, which also took into account the characteristics of the subjects, nature of toxicities, relevant external results. Another goal of this monitoring was to review the number of events needed for the primary analysis and whether the sample size needed to be adjusted to achieve the targeted number of events.

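### By-arm DFS looks could inform early termination or reporting, but no efficacy rule is stated, so the 5% error is not assured for the design as a whole

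*Protocol*

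**What the plan says.** **Planned look.** Protocol 12.3 schedules two interim analyses. The first is for safety. The second comes once 540 patients (or the cohort from the first analysis) have 3 years of follow-up. The Protocol Summary describes it as "The second analysis will look at safety as well as DFS and OS", and 12.3 applies the analysis method of section 12.2 to the primary endpoint. No event count is attached to it.

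**Further looks.** Protocol 12.3 adds that "periodic review of safety data (in the same format of the first interim analysis) will be performed for annual DMC meetings", and then "Efficacy data will not be included unless requested by DMC". SAP 4.8 puts it differently: "Interim analyses were scheduled every year as long as there is subject still on study treatment". It also records that "Subsequent reviews of DFS and OS were done upon request of DMC". These looks were comparative: "Treatment allocations in all the interim analyses were masked with the label" Group A and Group B.

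**Use of the results.** Protocol 12.3: "The analysis results of the interim analyses will not be the sole criteria for deciding whether to terminate accrual or report the results early". They are a guideline, weighed with patient characteristics, toxicity and external results. SAP 4.8 keeps early termination as a possible use but does not mention early reporting.

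**Error rate.** Protocol 12.1 derives 300 events from a two-sided 5% log-rank test with 80% power at HR 0.72. SAP 4.1 takes p<0.05 as significant, and SAP 4.9 triggers the final analysis at 300 events with at least 1 year of follow-up. Neither mentions an adjustment for interim looks. Protocol section 20 names 12.3 as the detailed plan for DMC review.

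**The concern.** A by-arm DFS comparison that may feed a decision to stop or report early is a test, whether or not it is called one. If a favourable interim result can be turned into an efficacy claim, each look is another chance of a false positive. The single-test 5% then no longer describes the trial. The usual protection is a boundary, a spending function, or a statement that interim looks cannot support an efficacy claim. None of these appears in either document, and the number of looks is open-ended.

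A reader of this confirmatory trial therefore cannot tell whether a DFS look could have produced an efficacy claim, or at what threshold.

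**Working it through.** **1. The plan's own figures.** Inputs from Protocol 12.1: HR 0.72, two-sided 5%, 80% power; allocation is 1:1.
- Schoenfeld: 4(1.960+0.842)²/(ln 0.72)² = 291 events.
- Freedman: (1.72/0.28)²(1.960+0.842)² = 297 events.
- Sample size: 300/0.21/0.90 = 1587, from 79% pooled DFS at 5 years and 10% attrition.

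Both event counts are within 3% of 300. These are single-test calculations with no allowance for interim looks.

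**2. Where the planned look falls.** The documents give no event count, so this rests on assumptions: exponential DFS with 79% at 5 years, and no attrition. The hazard is −ln(0.79)/5 = 0.0471 per year.
- 540 patients at exactly 3 years: 540 × (1 − 0.868) = 71 events.
- Later patients: 600-660 (1140 or 1200 minus 540; the 1140 comes from Protocol 12.1, "after enrollment of at least 1140 patients and 3-years follow-up being completed in 430 patients"). With follow-up uniform over 0-3 years the event probability is 0.0675, which gives 40-45 events.
- Total 112-116, or 37-39% of 300.
- If instead the 540 entered evenly over 2-3 years and the last of them has reached 3 years, they contribute 93-103 events. The total is then 133-147, or 44-49%.

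**3. Overall error if nominal p<0.05 could be acted on at every look.** Sequential log-rank Z statistics have correlation √(tᵢ/tⱼ), where t is the fraction of 300 events. The overall error is the probability under no effect that |Z| exceeds 1.96 at any look or at the final test.

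| Interim looks (fraction of 300 events) | Two-sided error | False aspirin benefit |
|---|---|---|
| none | 5.0% | 2.5% |
| 35% | 8.8% | 4.4% |
| 37% | 8.7% | 4.4% |
| 49% | 8.3% | 4.2% |
| 60% | 8.0% | 4.0% |
| 35%, 55% | 10.7% | 5.3% |
| 35%, 50%, 65%, 80% | 12.6% | 6.3% |

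**4. Same calculation with |Z|>3.29 (two-sided p<0.001) at interims and 1.96 at the final test.** The overall error is 5.0-5.1% for these schedules. With eight interim looks, at 20% to 90% in steps of 10%, it is 5.15%. That figure also bounds the error if the DMC's choice among those times depends on the data.

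**5. Price of the stricter threshold.**
- Power: the drift is −ln(0.72) × √(300/4) = 2.845. Power is Φ(2.845 − 1.960) = 81.2% for the fixed design, and 81.2% with the rule.
- Boundary HR = exp(−2z/√d). At 105 events it is 0.53 for p<0.001 and 0.68 for p<0.05. At 150 events it is 0.58 and 0.73.
- Chance of crossing p<0.001 at one look if the true HR is 0.72, Φ(2.845√t − 3.29): 5.4% at 35% of events, 10.0% at 50%, 13.9% at 60%.

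**6. Can a later spending rule repair past looks?** Suppose p<0.05 was actionable at one look at 50%, and the final level is then reset to 0.0490 by O'Brien-Fleming-type spending. The overall error is still 8.2%. The four-look schedule spends 11.1% at the interims alone, so no final level recovers 5%.

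**The case against.** The strongest reply is that the inflated figures assume a rule found in neither document. Protocol 12.3 says interim results are weighed with other evidence; it does not say that p<0.05 is enough. SAP 4.1 is a general convention. The two-look and four-look schedules are illustrations. There are also real safeguards: apart from safety, the trial size may not fall below 1200; interim results stay with the study statistician and the DMC; the DMC only makes recommendations; and SAP 4.9 still plans the analysis at 300 events. Nothing shows that an early claim was made.

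All of this is fair, and it is why the error is called not assured rather than exceeded. But the safeguards are not a decision rule. The 1200 minimum limits stopping of accrual, not early reporting, and masked labels hide direction but not a p-value.

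The timing in step 2 can also be questioned. If enrolment had reached 1587 by the planned look, the 1047 later patients would add about 71 events. The total would be 142-174, or 47-58% of 300, and the error at 58% is 8.0%, still inside the stated range. With the earlier planning rate (65% at 3 years, HR 0.72), 540 plus 600 patients give about 265 events (88%) and an error of 6.6%. The protocol has replaced that rate with the observed 79%.

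Two further points stand. A threshold written now cannot govern looks already done, and p<0.001 is one of several valid rules. Also, the 5% for the final test presumes the single primary endpoint in the SAP, whereas Protocol section 3 lists two primary DFS endpoints.

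**Conclusion.** The concern holds. The documents allow an unstated number of by-arm DFS looks to inform early termination or, in the protocol, early reporting, and they give no efficacy threshold. The final test alone keeps its 5% under the SAP's single primary endpoint. The error of the whole design lies between 5%, if no look could lead to a claim, and 8.0-12.6% in the schedules examined, if nominal p<0.05 could. The planned look by itself gives 8.7-8.3% at 37-49% of events under the exponential, no-attrition assumptions.

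The omission is certain. The size is conditional on a use of the looks that the documents leave open. It is a cheap improvement rather than a demonstrated error.

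**What to change.** In Protocol 12.3 and SAP 4.8:

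1. State that early stopping or reporting for DFS efficacy, at any planned or requested look, requires two-sided p<0.001, and that the final test stays at 0.05. Applying the same threshold to OS would be a harmless extension. People who have not seen by-arm results should adopt the rule.
2. For looks already done, report how many DFS reviews there were, the events at each, and whether any could have led to an efficacy claim and at what threshold. If none could, the final 0.05 stands. If one could, report the resulting overall error as a limitation. Do not reset the final level by retrospective spending, because it does not restore 5%.
3. Use the same terms in both documents for annual safety reviews and for DFS/OS looks.

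**Cost.** This needs wording for future looks and a DMC record of past ones. The 300-event target and the 81.2% power are unchanged. The downside is that a moderate interim benefit cannot be reported early: the observed HR would have to be about 0.53 or lower at 105 events, or 0.58 or lower at 150. If the true HR is 0.72, one look would cross with a probability of only about 5-14%.
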